3.0 STUDY DESIGN

3.1 Description of Study Design

Approximately 30 habitual soft contact lens wearing subjects will be enrolled in this two-hour randomized, contralateral, double-masked (subject and investigator masked), repeated measures dispensing study. All subjects will be seen for a Screening/Dispensing Visit at which informed consent will be obtained and eligibility will be assessed. If subjects satisfy all eligibility criteria and none of the exclusion criteria, subjects will be dispensed study lenses according to unique randomization schedules that will be provided to each Investigator.

There are two study lenses (one test and one control). Each subject will receive a pair of study contact lenses that will be worn for approximately 2 hours (test lens in one eye and control lens in the other eye). Subjects will complete a minimum of 1 study visit and a maximum of 2 study visits.

Visit 1: Approximately 20 minutes

Visit 2: Approximately 15 minutes

Both study visits will occur on the same day.

The clinical investigation will take approximately 2 weeks to complete.

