4.3 Instructions for Use and Administration

The Investigator and subjects will be masked to the study lenses. Unmasked study personnel will be responsible for dispensing and collecting the study materials and accountability. The randomization schedule will be created prior to the start of the study by an unmasked statistician not otherwise involved in the study.

Subjects will be receiving each of the study lens types once, in a randomized order. The subject will wear the study contact lenses for approximately 2 hours (Test lens in one eye and Control lens in the other eye). See Appendix B for additional Instructions for Use.

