5.1 Study Visits

5.1.1 METHODOLOGY:

Visit 1, Insertion

- Subjects will have at least an 8 hour no lens washout period prior to their insertion visit.
- Limbal and bulbar redness, corneal and conjunctival staining will be assessed with the slit lamp.
- Percent area staining covered will be assessed for all 5 quadrants of the cornea.
- A baseline spherical refraction will be performed, through which High Contrast/High Illumination (HCHI) logMAR visual acuity will be measured at 6m.
- Each subject will insert a randomized lens pair.
- Evaluate: sting/burn, dryness, comfort after 3 minutes of lens wear, centration, movement, wettability, deposits and preference based on comfort.
- Spherical over-refraction will be performed through which HCHI logMAR visual acuity will be measured at 6m.
- The subject will be instructed to wear the lens pair for approximately 2 hours.

Visit 2, Follow-up After 2 Hours of Lens Wear

- Spherical over-refraction will be performed through which HCHI logMAR visual acuity will be measured at 6m.
- Evaluate: sting/burn, dryness, comfort, preference for comfort, centration, movement, wettability, deposits and preference based on comfort.
- Limbal and bulbar redness will be re-assessed.
- Lenses will be harvested, stored dry in a standard case.
- Corneal and conjunctival staining will be re-assessed with the slit lamp.

- Percent area staining covered will be assessed for all 5 quadrants of the cornea.
- Digital photos of the cornea, conjunctiva, and lenses in situ may be acquired.

Grading scales for the biomicroscopic evaluations and subject assessments are according to applicable Research Clinic procedures. See Appendix A: Methods of Clinical Evaluation.

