7.4 Randomization

To minimize or avoid bias, subjects will be assigned randomization numbers as they are enrolled according to unique randomization schedules created for the study. The randomization schedule will be produced prior to study enrollment. Subjects will be receiving each of the study lens types once, in a randomized order. An effort will be made to conceal the CTM materials from the subject and the investigator throughout the study. Both the study subject and investigator will be masked.

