7.6 Statistical Analysis

Continuous data will be summarized using descriptive statistics: n, mean, standard deviation, median, minimum and maximum. Categorical data will be presented by the total counts for each category and corresponding percentages. The data for each of the ordinal dependent measures (i.e., those assigned a clinical grade) will be analyzed using appropriate nonparametric techniques. Unless otherwise noted, paired t tests will be used to test for

differences in means for each of the parametric dependent variables. Differences at the $p \leq 0.05$ level will be considered statistically significant.

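### Section 7.4 does not say that the test-lens eye is randomised in balance, and the paired t test in 7.6 does not use the assignment: a valid analysis that gives up some precision

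*Combined protocol and SAP*

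**What the plan says.** Section 3.1 describes subjects "enrolled in this two-hour randomized, contralateral, double-masked", with the "test lens in one eye and control lens in the other eye"; section 4.3 repeats this. Section 5.1.1 adds: "Each subject will insert a randomized lens pair". None of these sections says outright that the eye is what is randomised.

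Section 7.4 says that "subjects will be assigned randomization numbers as they are enrolled according to unique randomization schedules created for the study", and that "Subjects will be receiving each of the study lens types once, in a randomized order". It gives no allocation ratio, blocking or right/left balance. On timing it says: "The randomization schedule will be produced prior to study enrollment".

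Section 7.6 says "Unless otherwise noted, paired t tests will be used to test for" differences in means of the parametric variables, and it plans nonparametric methods for graded measures. Neither analysis uses the eye that received the test lens. Section 7.6.3 plans no exploratory or sensitivity analysis, so no eye-adjusted result appears elsewhere.

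Three other provisions bear on balance. Discontinued subjects are not replaced (3.2.3), an adverse event leads to discontinuation (6.0), and non-safety summaries use eligible completers only (7.5).

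**The concern.** Two lenses worn at the same time have no order of wear. The useful content of the schedule is therefore the eye: test right and control left, or the reverse. Suppose that acuity or a rating differs systematically between right and left for reasons unrelated to the lens. That difference then enters the test-minus-control difference with a plus sign in one assignment group and a minus sign in the other.

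A one-sample paired t test pools the groups. With an equal split the right-left difference cancels from the mean but stays in the SD. With an unequal split part of it also stays in the mean. The loss is of precision and, for a particular unequal split, of accuracy, measured against the 0.05 logMAR margin in 7.2. The design already generates the information that would remove both.

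**Working it through.** **Inputs from the documents.** SD 0.069, 80% power and 15 subjects (7.3); margin 0.05 (7.2); about 30 enrolled (3.1); 0.02 logMAR per letter (Appendix A, 1.1).

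**Assumptions.** 0.069 is the SD of paired differences without eye noise (7.3 does not say which SD it is). All 30 subjects are analysed. The systematic right-minus-left difference e is 0.02 to 0.04, that is, one to two letters.

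**The plan's own figure.** n = [0.069 × (1.960 + 0.842)/0.05]² = 14.95, so 15. This reproduces the stated size as a paired, two-sided 5% normal approximation.

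**Model.** D = τ + s·e + error, where D is test minus control, τ is the lens effect, and s = +1 if the test lens is in the right eye and −1 if in the left.

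**Standard error with a 15:15 split.** The expected variance of D is 0.069² + e² × 30/29.

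| e | SD of D | SE | Ratio to 0.069/√30 = 0.0126 | Equivalent loss of subjects |
|---|---|---|---|---|
| 0.02 | 0.0719 | 0.0131 | 1.04 | 8% |
| 0.04 | 0.0801 | 0.0146 | 1.16 | 26% |

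The last column is 1 − (0.069/SD of D)².

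**Power to rule out 0.05** (noncentral t, one-sided 5%, n = 30; 28 df with the eye term, 29 without):

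| True difference | With eye term | Without, e = 0 | Without, e = 0.02 | Without, e = 0.04 |
|---|---|---|---|---|
| 0 | 98.7% | 98.7% | 98.1% | 95.5% |
| 0.02 | 75.1% | 75.2% | 72.1% | 64.0% |

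The loss is 0.6 to 3.2 points at a true difference of 0 and 3.0 to 11.1 points at 0.02. If e = 0, the extra term costs about 0.1 point. The noncentral t counts e as random error, which matches unblocked assignment. Simulating a fixed 15:15 split (200,000 runs) gives slightly smaller losses, because e then cancels from the mean: power without the term is 98.4% and 97.5% at 0, and 72.8% and 66.1% at 0.02.

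**Shift when the split is unequal:** e(nR − nL)/n.

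| Split of 30 | e = 0.02 | e = 0.04 |
|---|---|---|
| 16:14 | 0.0013 | 0.0027 |
| 18:12 | 0.0040 | 0.0080 |
| 20:10 | 0.0067 | 0.0133 |

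The 20:10 shifts are 13% and 27% of the margin. If the schedule is unblocked, 20:10 or worse has probability 9.9% (binomial, 30 subjects, 0.5).

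**Type I error of the two-sided 5% test of no difference** (100,000 simulated runs; e = 0.02 / 0.04): 4.2% / 2.4% at 15:15, 5.2% / 5.2% at 18:12, 6.9% / 11.3% at 20:10, and 5.1% / 5.1% averaged over simple randomisation.

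**Cost of the eye term under imbalance.** The adjusted SE is 0.069 × ½√(1/nR + 1/nL). At 20:10 this is 0.0134 against 0.0126, about 6% more, in exchange for removing the shift.

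**The case against.** The planned test is valid. Over random assignment it is unbiased and holds about 5% type I error, and with an equal split it is conservative. A reader might infer that the paired t test is a biased analysis. The documents do not support that: the shift is conditional on one realised split, and nothing shows that the schedule is unbalanced. Silence on blocking in 7.4 is not evidence that blocking is absent. This stands.

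A reader might also infer that every right-left difference contaminates the primary endpoint. That does not follow either. The endpoint is normalised acuity, a term that the plan does not define, and acuity is measured before insertion. If normalising means relative to each eye's baseline, a stable right-left difference cancels. The 3-minute comfort and sting/burn ratings have no pre-lens baseline in the plan, so normalisation gives no such protection there.

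The size of e is assumed, and no section says that one eye is always inserted or tested first. If that order varies between subjects, a right/left term does not remove its effect. The 0.069 may already contain eye noise; the term would then recover precision rather than prevent a further loss.

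Finally, 30 subjects is twice the calculated 15, and 7.6.1 sets no pass/fail criterion, so a small shift changes no prespecified decision. This limits the priority but does not remove the point. A balanced schedule can still yield an unequal set of completers, and the adjustment costs almost nothing when e = 0.

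**Conclusion.** The point holds as a minor improvement to a valid analysis. The firm textual gap is in 7.4: a randomised order does not describe lenses worn together, and neither randomisation of the eye nor its balance is stated. The analysis gap is that 7.6 leaves the assignment unused.

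The gain is modest. At one letter it is about 4% in the standard error and less than one point of power at a true difference of 0. At two letters with a true difference of 0.02 it reaches 16% and about 11 points. These figures depend on the assumed e, on 0.069 being the SD of differences without eye noise, and on e surviving normalisation. Protection against an unequal split is a second, smaller benefit. The shift of 0.007 to 0.013 needs a 20:10 split, which is uncommon even without blocking.

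**What to change.** **Section 7.4:** replace the reference to order with a statement that the eye receiving the test lens is randomised, in balanced blocks, so that right and left are assigned equally often.

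**Section 7.6, parametric measures:** regress the test-minus-control difference on the eye that received the test lens, coded +1 for right and −1 for left, and report the intercept as the lens effect. This equals the simple mean of the two assignment-group means. Keep the ±1 coding and do not re-centre it at the sample mean; otherwise the intercept is again the unadjusted mean and the shift returns.

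**Section 7.6, ordinal measures:** compare right-minus-left differences between the two assignment groups with a rank-sum test. The groups differ by twice the lens effect, and a common right-left effect drops out.

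Insertion- and testing-order effects are removed only if that order is tied to right/left, so the plan should state whether it is.

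**Cost:** a few sentences, one degree of freedom, and no new data or subjects.

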Statistical Methods: Continuous data will be summarized using descriptive statistics: n, mean, standard deviation, median, minimum and maximum. Categorical data will be presented by the total counts for each category and corresponding percentages. The data for each of the ordinal dependent measures (i.e., those assigned a clinical grade) will be analyzed using appropriate nonparametric techniques. Unless otherwise noted, paired t tests will be used to test for differences in means for each of the parametric dependent variables. Differences at the $p < 0.05$ level are considered to be statistically significant.

Sample Size Calculations: In a previous study with similar lenses (ROC2-16-032), the standard deviation for logMAR VA was 0.069. A sample size of 15 subjects was calculated to have a study power of 80%.

Table of Contents

INVESTIGATIONAL SITE AND STUDY PERSONNEL.....	2
SYNOPSIS.....	3
1.0 INTRODUCTION	10
2.0 OBJECTIVE	10
3.0 STUDY DESIGN.....	10
3.1 Description of Study Design.....	10
3.2 Selection of Study Population.....	10
3.2.1 Eligibility	11
3.2.1.1 Inclusion Criteria	11
3.2.1.2 Exclusion Criteria	11
3.2.2 Point of Enrollment and Randomization.....	11
3.2.3 Subject Completion.....	11
3.2.4 Lost to Follow-up.....	12
3.3 Investigators.....	12
3.4 Study Duration	12
3.5 Protocol Changes and Amendments	12
4.0 STUDY MATERIALS	13
4.1 Description of the Test Article(s) (Study Lenses)	13
4.2 Description of Comparator Product(s) (Control Lenses).....	13
4.3 Instructions for Use and Administration.....	13
4.3.1 Storage Requirements	13
4.3.2 Subject Instructions.....	13
4.4 Other Study Materials	14
4.5 Packaging and Labeling	14
4.6 Accountability.....	14
4.7 Masking.....	14
4.8 Product Replacement	14
4.9 Risk Assessment	14
4.9.1 Risk Related to Subject.....	15
4.9.2 Risk Related to Data Management	15
4.10 Relevance of Clinical Investigation.....	15
5.0 STUDY METHODS.....	16
5.1 Study Visits	16

5.1.1 METHODOLOGY:	16
5.1.2 Unscheduled Visits	17
5.1.3 Missed Visits.....	17
5.1.4 Post-Study Follow-up Visit	17
5.2 Study Completion	17
5.2.1 Study Termination/Suspension	17
5.2.2 Study Termination Procedure	18
5.3 Concomitant Medications/Therapy.....	18
5.4 Protocol Deviations.....	18
6.0 ADVERSE EVENTS (AE).....	18
6.1 Adverse Event Definitions.....	18
6.1.1 Adverse Event (AE).....	18
6.1.2 Serious Adverse Event (SAE).....	19
6.1.3 Serious Adverse Ocular Event	19
6.1.4 Significant, Non-Serious Adverse Event	20

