7.0 STATISTICAL METHODS

7.1 Study Endpoints

Primary Endpoint:

1. Normalized logMAR Visual Acuity

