7.3 Sample Size

Previous clinical experience with samfilcon A lenses is useful to provide an adequate sample size for this investigation. Too few subjects will lead to a decrease in study power. The power of a study indicates the chance of making a Type II error (i.e. showing no statistical difference even though a difference actually exists). A study power of 100% would require an infinite number of subjects. In clinical studies it is generally acceptable to use a power as low as 80%, which is a good compromise between number of subjects and the risk of not detecting a true difference that exists. The Type I error rate (i.e. chance of finding a statistical difference that really doesn't exist) is typically set at 5% ($p=0.05$) chance.

In a previous study with similar lenses (ROC2-16-032), the standard deviation for logMAR VA was 0.069. A sample size of 15 subjects was calculated to have a study power of 80%.

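### Section 7.6 gives every measure compared at 0.05 the same significance label as the primary, with no hierarchy, adjustment or descriptive status for the rest

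*Combined protocol and SAP*

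**What the plan says.** Section 7.1 lists one endpoint, "Normalized logMAR Visual Acuity", without a visit. Section 7.2 sets its hypothesis around a margin of 0.05 logMAR.

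Section 7.6 applies nonparametric methods to each graded measure. For each parametric variable, "paired t tests will be used to test for" differences in means. One rule then covers all of them: differences at the p ≤ 0.05 "level will be considered statistically significant". The synopsis has the same rule with a strict inequality: "Differences at the $p < 0.05$ level are considered to be statistically significant".

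The measures are listed in section 5.1.1. At 2 hours, for example: "Evaluate: sting/burn, dryness, comfort, preference for comfort, centration, movement, wettability, deposits and preference based on comfort". VA, redness and staining are added to that list, and Appendix A splits several items into sub-scales.

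Section 7.3 says of the Type I error rate that it "is typically set at 5% ($p=0.05$) chance". Section 7.6.1 says there are no pass/fail criteria, and section 7.6.3 plans no exploratory analyses. No section ranks the non-VA measures, adjusts for their number or calls their p values descriptive.

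**The concern.** The objective in section 2.0 is clinical performance, which is wider than acuity. Readers will therefore look at staining, redness, sting/burn, comfort and wettability as well as VA. Under 7.6 a difference on any of these, or in nasal lens overlap, earns the same label as the primary result.

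With many comparisons and no ranking, two things can go wrong. A chance difference can be reported as a finding, and about half of chance differences would favour the test lens. A real difference in staining or sting/burn can also be dismissed as one of the chance results to be expected, because nothing in the plan sets it apart. As there are no pass/fail criteria, the significance label is the only interpretive rule the plan offers.

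**Working it through.** **1. What the 5% in 7.3 refers to.** Inputs: SD 0.069, 80% power and 15 subjects (7.3); difference 0.05 (7.2). Assumptions: two-sided 5%, and 0.069 is the SD of the paired difference.

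n = ((1.960 + 0.842) × 0.069 / 0.05)² = 14.95, rounded up to 15.

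The plan's figure is reproduced. The 5% fits the error rate of a single VA comparison.

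**2. How many comparisons 7.6 covers.** The documents give no number, so this is a count from 5.1.1 and Appendix A.

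- After insertion: VA 1, sting/burn 1, dryness 1, comfort 1, centration 4 (one grade and three directions in mm), movement 1, wettability 2, deposits 1. Total 12.
- At 2 hours: the same 12, plus limbal and bulbar redness 2, corneal staining severity and extent 2, percent area in five sectors 5, conjunctival staining severity and extent 2. Total 23.
- Sum: 12 + 23 = 35, without preference or baseline.

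Other countings:

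- One test per item named in 5.1.1, with five sectors: 8 + 17 = 25.
- The same with the sectors as one item: 21.
- 35 plus preference at each visit: 37.
- 37 plus 12 baseline findings (VA and the 11 redness and staining items): 49.

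**3. False positives if the lenses are identical and every test has true size 0.05.** The expected number is 0.05k, whatever the correlation. The chance of at least one, if independent, is 1 − 0.95^k.

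| Comparisons k | Expected false positives | At least one, if independent |
|---|---|---|
| 21 | 1.05 | 66% |
| 25 | 1.25 | 72% |
| 35 | 1.75 | 83% |
| 37 | 1.85 | 85% |
| 49 | 2.45 | 92% |

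**4. Effect of correlation.** The documents give no correlations, so a range is assumed. For 35 two-sided normal statistics with common correlation ρ, the chance of at least one is 1 − E[{Φ((1.96 − √ρ·U)/√(1−ρ)) − Φ((−1.96 − √ρ·U)/√(1−ρ))}^35], with U standard normal.

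| ρ | 0 | 0.3 | 0.5 | 0.7 | 0.9 |
|---|---|---|---|---|---|
| At least one of 35 | 83% | 71% | 54% | 36% | 18% |

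**5. Direction.** If independent, the chance of at least one false result favouring the test lens is 1 − 0.975^35 = 59%.

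**6. The primary itself.** VA is measured with lenses on at both visits and 7.1 names neither. If both are tested at 5% and either may be claimed, the rate is up to 1 − 0.95² = 9.75%.

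**The case against.** The strongest reply is that this is a small study with no pass/fail criteria, so no decision in the plan turns on any of these p values. Full descriptive summaries are planned. Clinically important staining is picked out by grade (Grade 3 or above in 6.1.4), not by a p value. That stands, and it limits the weight of the point.

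The calculation can also be challenged, and these challenges stand too:

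- The count is an inference. Section 5.1.1 names centration and wettability once each per visit, and 7.6 does not say that every sub-scale is tested at every visit.
- The measures are surely correlated: the same items two hours apart, five sectors of one cornea, severity and extent of the same staining. The 83% is an upper illustration.
- Many grades run from 0 to 4 in eyes required to be normal, so ties are likely. With five discordant pairs, the smallest two-sided exact sign-test p value is 2 × 0.5⁵ = 0.0625, so that test could not reach 0.05. Heavy ties would lower the false-positive rate.

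A further reply is that a false positive on a difference test only works against the sponsor, by suggesting that the lenses differ. This holds only in part, because about half of such results would favour the test lens.

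A reader might infer that the 5% in 7.3 is a study-wide promise that the plan breaks. The text does not support this. It says "The Type I error rate (i.e. chance of finding a statistical difference that really doesn't exist) is typically set at 5" percent, in a general explanation of power that leads into the VA sample size. Each comparison keeps its own 5%, and the extra tests do not inflate the error of one primary test.

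**Conclusion.** The point holds as a defect in labelling. Section 7.6 extends one unqualified significance rule to some 21 to 49 comparisons, of which only VA has endpoint status. With 35 comparisons and identical lenses, 1.75 false significant differences are expected. The chance of at least one ranges from 83% (independence) to about 18% (common correlation 0.9). These figures assume a true size of 0.05 for every test, and the correlations are assumed.

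Two stronger conclusions are tempting but not supported. One is that a false significant result is more likely than not: at correlations of 0.7 and 0.9 the chance is below one half. The other is that the results could not be interpreted: descriptive summaries and grade-based safety criteria remain, and no pass/fail decision depends on the tests.

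The primary has its own, smaller gap. Without a named visit, its error rate can reach 9.75%. The change should be made, but the study does not depend on it.

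**What to change.** - **7.1:** name one of the two lens-on visits for the primary VA comparison.
- **7.6:** reserve the term *statistically significant* for that comparison, and state that it is tested against the 0.05 margin in 7.2. The paired test of a zero difference does not address that hypothesis.
- **7.6:** report all other measures as paired differences with 95% confidence intervals, or counts for grades, with p values labelled nominal. Keep ocular findings listed in full whatever their p value.
- **Synopsis and 7.6:** use the same inequality at 0.05.

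A fixed testing order for secondary endpoints is not advised. It would conflict with keeping the label for VA alone. If it opened with a VA difference test, a non-significant VA result would stop it before staining or sting/burn was reached.

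The cost is wording only, with no new subjects, visits or data. The downside is that a difference on any measure other than VA, even a real one, can be reported only as nominal.
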